4.0 LIST OF ABBREVIATIONS AND DEFINITIONS OF TERMS

Abbreviation	Term
AE	adverse event
aPTT	activated partial thromboplastin time
AUC	area under the concentration-time curve
β-hCG	beta human chorionic gonadotropin
BPS	bladder pain syndrome
CRA	clinical research associate
CRF	case report form
DMSO	dimethyl sulfoxide
ECG	electrocardiogram
FDA	Food and Drug Administration
GCP	Good Clinical Practice
HCl	hydrochloride
IC	interstitial cystitis
IC/BPS	Interstitial cystitis/bladder pain syndrome
ICF	informed consent form
ICH	International Conference on Harmonisation
IDMC	independent data monitoring committee
IEC	independent ethics committee
INR	international normalized ratio
IRB	institutional review board
IxRS	interactive voice or web response system
MedDRA	Medical Dictionary for Regulatory Activities
NRS	numerical rating scale
PORIS	Patient Overall Rating of Improvement of Symptoms
PT	prothrombin time
PUF	Pelvic Pain and Urgency/Frequency
RBC	red blood cell
SAE	serious adverse event
SAP	statistical analysis plan
SOC	system organ class
SPID-12	sum of pain intensity differences from baseline to 12 hours
SPID-24	sum of pain intensity differences from baseline to 24 hours
SUID-12	sum of urgency intensity differences from baseline to 12 hours
SUID-24	sum of urgency intensity differences from baseline to 24 hours
TEAE	treatment emergent adverse event
USP	United States Pharmacopeia
WBC	white blood cell

5.0 ETHICS

This study will be conducted in compliance with the following: the protocol; Food and Drug Administration (FDA) regulations; International Conference on Harmonisation (ICH) E6, Guideline for Good Clinical Practice; and all other applicable local laws and regulatory requirements. Each study site will seek approval by an institutional review board (IRB) or according to regional requirements. The IRB will evaluate the ethical, scientific and medical appropriateness of the study. Furthermore, in preparing and handling case report forms (CRFs), the investigator, subinvestigator, and the site staff will take measures to ensure adequate care in protecting subject privacy. To this end, a subject number and subject identification code will be used to identify each subject.

5.1 INFORMED CONSENT

All subjects will have the purpose of the study, study interventions and evaluations, and the potential risks and benefits of participation explained to them and any questions will be answered. If a subject consents to participation in this study, the subject will review and sign the informed consent form (ICF).

Written informed consent will be obtained from all subjects (or their guardian or legal representative, as applicable for local laws). Consent will be documented on a written ICF. The ICF will be approved by the same IRB that approves this protocol. Each ICF will comply with the following: the FDA regulations in Title 21 Code of Federal Regulations, Part 50; ICH; Good Clinical Practice (GCP); and local regulatory requirements. The investigator agrees to obtain approval from the sponsor of any written ICF used in the study, prior to submission to the IRB.

Investigators may discuss study availability and the possibility for entry with a potential subject without first obtaining informed consent. However, informed consent must be obtained and documented prior to initiation of any procedures that are performed solely for the purpose of determining eligibility for this study, including withdrawal from current medication(s).

Once appropriate essential information has been provided and fully explained in layman's language to the subject by the investigator or by a qualified designee, the IRB-approved written ICF will be signed and dated by both the subject and the person

obtaining consent (investigator or designee), as well as by any other parties required by the IRB. The subject will receive a copy of the signed ICF; the original will be kept on file by the investigator.

6.0 INVESTIGATORS AND STUDY PERSONNEL

This study will be conducted by qualified investigators under the sponsorship of Urogen N.A, Inc. (Urogen), at approximately 30 investigational sites in the United States and Canada.

The name and telephone and fax numbers of the medical monitor and other contact personnel at the sponsor and of the contract research organization(s) are included in the Investigator Study Files provided to each site.

7.0 INTRODUCTION

7.1 BACKGROUND

Interstitial cystitis/bladder pain syndrome (IC/BPS) is a disease considered rare as late as 1990. The hallmarks of the disease are frequency and urgency of urination, and bladder pain of simply pelvic origin. As knowledge of the disease and its symptomatology increase, the reported prevalence increases. In 1990 it was thought that 60,000 to 80,000 women in the United States had IC¹. In 1997, it was thought to be approximately 500,000 to 1,000,000⁴. Estimates as high as one in four women can be made when utilizing a questionnaire that encompasses a more complete battery of IC symptoms^{1,7}. This increase in reported prevalence is primarily due to a change in awareness of the disease. Traditionally, IC was diagnosed only in severe patients with a destroyed bladder, and considered to be relatively rare. It is currently widely accepted that IC includes many patients with mild, intermittent, and severe forms of the disease^{7,8}. Most patients with IC have low-grade bladder symptoms (3 on a scale of 0 to 10) punctuated by intense flares of 8 to 10 out of 10 that last from 3 days to 3 weeks and may occur infrequently or as often as five to eight times per year. These flares are often incorrectly diagnosed.

Currently, since many of these IC flares are misdiagnosed as urinary infections in women and often as prostatitis in men, several billion dollars in treatments are inappropriately prescribed to these patients that offer no relief.

For the unfortunate patient with severe disease living daily with pain scores of 8, 9, or 10 out of 10, there is little or no relief or effective therapy available to relieve these intense symptom flares. Drugs such as pyridium and urelle offer minimal urinary analgesia. Anticholinergic and antimuscarinic compounds have limited or no success in the treatment of pain in IC/BPS.

Opiates have been utilized but have limited success and are not optimum drugs to employ. Because opiates can, in time, upregulate sensory nerves due to dependency, the patient's pain will become resistant relatively quickly as tolerance to the drug grows; the patient will become addicted to the medications. In addition, opiates can significantly impair a patient's mental faculties, and overall functioning will be markedly affected. Neural stimulators such as Interstim® might help temporarily with frequency and urgency, but have little or no activity on small unmyelinated C fibers

(pain fibers) because they do not originate in the sacral nerves being stimulated. Patients who are considered to be surviving this disease have a quality of life reported to be worse than that of dialysis patients and unfortunately many have committed suicide¹⁶.

There are currently two FDA-approved therapies for the symptoms of bladder pain of IC: oral Elmiron® capsules (pentosan polysulfate sodium) and intravesical RIMSO®-50 and its generics (50% dimethyl sulfoxide [DMSO]).

Elmiron is a synthetic heparinoid-like molecule that is thought to work by augmenting the mucus layer with heparin and, thus may provide a physicochemical barrier to the penetration of the urinary solutes to the bladder wall²¹. According to the product label, the efficacy of Elmiron was evaluable at 3 months, with 38% of patients achieving greater than 50% improvement in bladder pain versus 18% for placebo-treated patients. In a dose-ranging study of Elmiron, Nickel et al.¹ observed a response rate of about 20% at 1 month of treatment that increased to approximately 60% at 8 months, resulting in their conclusion that chronic duration of therapy is more important than dosage.

Intravesical treatment with RIMSO-50 (50% DMSO) was approved by the FDA in 1978 for symptomatic treatment of IC. Its exact mechanism of action is unclear, and six to eight weekly bladder instillations are required. After each instillation, patients exhibit an unpleasant garlic-like odor, and the majority of patients complain of significant discomfort both during and after each treatment (RIMSO-50 product label). Perez-Marrero et al.¹¹ conducted a placebo-controlled study of 50% DMSO for IC, during which subjects received intravesical instillations of study drug or saline placebo every 2 weeks for two sessions of four treatments each. A total of 53% of DMSO treated patients exhibited “marked improvement” versus 18% for placebo treated patients. Nevertheless, most urologists view current IC treatment options as unsatisfactory, as exemplified by the Mayer et al.² statement: “Effective medical treatment for patients with moderate to severe IC remains elusive.”

Buffered lidocaine-heparin (intravesical instillation) URG 101, is proposed as an investigational new drug for the treatment of pelvic pain and urgency of bladder origin. All components of the investigational solution are currently FDA approved for other indications. Lidocaine Hydrochloride (HCl) is a local anesthesia for pain control during surgical procedures and for topical applications. Heparin sodium is an

anticoagulant for the prevention and treatment of thrombotic conditions such as pulmonary embolism and arteriovenous thrombosis. The proposed use of buffered lidocaine-heparin is based on both open-label clinical experience^{12,13}, and on Urigen's double-blind placebo-controlled study, URG101-101, in subjects with symptoms of pelvic pain and urgency. In this study, subjects experienced immediate symptom relief; improvement in urgency for drug versus placebo achieved statistical significance ($p = 0.006$) and trended to improvement in pain ($p = 0.093$). A recent, multisite, double-blind study using a single dose of URG101 versus placebo showed a significant reduction in pain and urgency ($p = 0.03$)²⁰.

URG101 (alkalinized lidocaine-heparin) is a combination therapy for relief of symptoms of pain and urgency associated with interstitial cystitis/bladder pain syndrome. The formulation is instilled directly into the bladder, with the lidocaine modulating bladder neural hyperactivity that is often associated with bladder pain and urgency, urge, and muscle spasms. Heparin (chemically similar to Elmiron, which is approved for IC) augments natural heparinoids on the surface of the urothelium to limit urinary potassium and other urinary toxins from penetrating to the underlying tissues.

Since the two FDA-approved therapeutics, RIMSO-50 and Elmiron, require chronic administration for any benefit to develop, there is no treatment for pain other than narcotics. Consequently, alkalinized lidocaine-heparin provides relief over both a short-term and medium-term time period, for which there is no current FDA-approved therapy. URG101 offers the first relief that is effective and that downregulates sensory nerves without rebound¹³.

We propose that URG101 will meet a serious need in this patient population for the following reasons: (1) the millions of people afflicted with IC; (2) no effective therapy for severe symptom flares; (3) reduced quality of life; (4) the wasted use of antibiotics to treat nonexistent infections; and (5) very real suicide threat in patients with severe symptoms.

[figure not shown]
7.2 URG101

The individual components of this combination therapy, Lidocaine HCl and heparin sodium, are FDA-approved products for use as a local anesthetic and an anticoagulant, respectively. It was demonstrated that when these components were mixed together and buffered by the addition of sodium bicarbonate, the resultant solution reduced symptoms of pelvic pain and urgency upon instillation into a subject's bladder¹². Most subjects exhibit both an acute benefit as well as sustained benefit from single and multiple treatments^{13,20}. This multimodal therapy achieves acute benefit for subjects who have no standard acute treatment for pelvic pain and urgency of bladder origin.

The rationale for this combination therapy is twofold. Lidocaine, a local anesthetic, traverses the urothelium when uncharged at alkaline pH, reversing the local neural hyperactivity of the bladder neurons and, thereby reducing the sensations of pain and urge, and also reducing muscle spasms. Heparin, a glycosaminoglycan, augments natural heparinoids that may be deficient on the surface of the urothelium. Heparinoids are part of the mucus layer of the urothelium and help to limit urinary solutes such as urea and potassium from penetrating to the underlying tissues thereby preventing pain, tissue inflammation, and muscle spasms²¹.

7.3 CLINICAL EXPERIENCE WITH URG101

Previously, URG101 was studied in open-label clinical studies at the University of California – San Diego¹³ and in a controlled Phase 2 multicenter trial sponsored by Urigen. These studies demonstrated that URG101 was safe and well tolerated. No serious adverse events (SAEs) or unexpected adverse events (AEs) or significant changes in blood coagulation were observed, demonstrating that heparin in the bladder does not appreciably enter into systemic circulation.

In the URG101-104 study, a multicenter, single-dose, cross-over, double-blind, placebo-controlled study, followed by one open label treatment, a total of 28 subjects were enrolled²⁰. The study was terminated early due to a recall of heparin with no suitable replacement, and the planned interim analysis became the final unblinded analysis. Statistical significance was achieved for the primary endpoint (i.e., average percentage change in pain from 0.5 to 12 hours), was 42% on URG101 compared with 21% on placebo ($p = 0.03$). Similar results were seen with the secondary endpoints of $\geq 50\%$ overall improvement ($p = 0.01$) and average percentage change in pain plus urge and urge alone ($p = 0.03$).

7.4

RISKS AND BENEFITS

The study drug components (Lidocaine Hydrochloride and Heparin Sodium) both have extensive previous human experience since their United States approvals in 1948 and 1939, respectively. Additionally, both of these drugs are normally administered via parenteral injection, whereas intravesical alkalinized lidocaine-heparin is administered into the lumen of the bladder and only comes into contact with the urothelium.

Lidocaine is a well-characterized small molecule drug used for local anesthesia. The uncharged form of lidocaine is able to traverse membranes and enter into systemic circulation. AEs are primarily dose-related upon reaching a 6- $\mu\text{g}/\text{mL}$ serum lidocaine concentration. The maximum recommended intravenous dose for adults is 300 mg, which is well above the 200 mg lidocaine dose in URG101. Additionally, intravenous lidocaine is also a class I antiarrhythmic and is often used simultaneously with intravenous heparin in the acute care setting after myocardial infarction. Heparin (a large, naturally sulfated polysaccharide) is an intravenous anticoagulant used for the prophylaxis and treatment of arterial or venous thrombosis and coagulopathies. Heparin's large size prevents it from being absorbed across epithelial surfaces.

The previous human experience of intravesical buffered lidocaine-heparin in the URG101-101 study involved 43 subjects on active drug. The intravesical instillation of buffered lidocaine-heparin (160 mg lidocaine, 40,000 units heparin, pH 7.8) did not alter the prothrombin time (PT) and activated partial thromboplastin time (aPTT) of these subjects, consistent with the heparin component not entering systemic circulation. Monitoring of serum lidocaine concentrations at 1 hour demonstrated

that the serum lidocaine concentrations were < 1.0 $\mu\text{g}/\text{mL}$ for most subjects (32 of 43), with only 11 subjects with serum lidocaine concentrations > 1.0 $\mu\text{g}/\text{mL}$, and the highest concentration of 1.5 $\mu\text{g}/\text{mL}$. In the URG101-104 study serum levels of lidocaine ranged from 0.24 to 2.0 $\mu\text{g}/\text{mL}$, with an average of 0.51 $\mu\text{g}/\text{mL}$, and neither the aPTT nor the PT was altered in any subject²⁰. These serum lidocaine concentrations are well below the toxic 6- $\mu\text{g}/\text{mL}$ concentration for lidocaine and changes in bleeding parameters have not been seen; therefore, the lidocaine and heparin in URG101 do not pose an unacceptable safety risk.

In summary, buffered lidocaine-heparin provides relief of bladder pain and urgency over both short-term and medium-term time periods, for which there is no currently FDA-approved therapy, and thus may be beneficial for individuals with chronic pelvic pain of bladder origin.

7.5 STUDY RATIONALE

7.5.1 Rationale for Dose

Intravesically administered heparin is safe because it is a large molecule, will not penetrate the bladder epithelium, and will not be observed systemically; therefore, it is in essence, a topical therapy. This was substantiated by the two Phase 2 clinical trials previously conducted by Urogen. A total of 90 subjects received a dose of 40,000 units of heparin, and 28 subjects received a total of 51 exposures to 50,000 units of heparin. Plasma INR and aPTT were unchanged after administration of drug in all subjects. In extensive experience at University of California – San Diego, the higher doses of heparin were more effective than the lower doses.

Unlike intravesically instilled heparin, lidocaine has potential toxicity if the serum concentrations exceed 6 $\mu\text{g}/\text{mL}$. In one reported trial¹⁷, up to 6 mg lidocaine (approximately 300 to 400 mg total dose) per kg of body weight was given to 12 subjects. Serum lidocaine concentrations were measured for 3 hours after administration. The highest serum concentration observed was 1.7 $\mu\text{g}/\text{mL}$, which was well below the level where symptoms may occur. In the Urogen Phase 2 studies, the highest lidocaine dose administered was 200 mg. In all subjects receiving the drug, lidocaine concentrations were < 2.0 $\mu\text{g}/\text{mL}$ which were well below the concentrations that are associated with safety issues. In the Urogen URG101-104 study, 50% of subjects experienced relief of symptoms (i.e., 50% reduction overall)

after a single administration of URG101 containing 50,000 units of heparin and 200 mg lidocaine²⁰. The placebo arm showed only an 11% reduction in symptoms. These data revealed the greatest difference in relief of symptoms between drug and placebo for any therapeutic trial conducted in IC. As a result of these data, 50,000 units of heparin combined with 200 mg lidocaine is the proposed dose for the Phase 2a URG101-105 study since excellent efficacy is seen at this dose, along with very safe serum lidocaine concentrations, no changes in bleeding parameters, and no significant symptoms or toxicities.

7.5.2 Rationale for Single Dose

The Urogen Study URG101-101 revealed a 51% placebo response rate. This was seen throughout the study, with the exception of one study site. This site enrolled subjects with severe IC/BPS, where the placebo response was 20% in keeping with prior studies with subjects with severe disease.

There is currently no effective therapy to relieve these intense symptom flares.

It is proposed, therefore, to perform a single-dose study to document the effectiveness of URG101 in relieving the intense flare in subjects with IC.

7.5.3 Rationale for Study Endpoint

Pain and urgency analog scales were used in the clinical trials that were the basis of the Elmiron approval and were reliable outcome measures¹⁶. The global assessment of symptoms (also known as the Patient Overall Rating of Improvement in Symptoms [PORIS] questionnaire) was also part of the basis for the ultimate FDA approval of Elmiron for sale in the United States. This endpoint was validated statistically¹⁹ and was found to be a sensitive and reliable outcome measure. This endpoint was also used for several therapeutic trials conducted by the National Institute of Diabetes and Digestive and Kidney Diseases clinical trials collaborative group¹¹. Both the analog scales and the PORIS questionnaire were utilized in Study URG101-104 with successful outcomes. For the proposed Phase 2a (Study URG101-105) clinical trial with URG101, the numerical rating scales (NRSs) for bladder pain will be employed

as the basis for the primary outcome measure, and the urgency NRS, the PORIS questionnaire and frequency will be used for secondary endpoints. Urination diaries will be collected for information purposes.

8.0 STUDY OBJECTIVES

8.1 PRIMARY OBJECTIVE

The primary objective of the study is as follows:

1. To evaluate the change in sum of bladder pain intensity differences from baseline to 12 hours (SPID-12) after administration of URG101 compared with the SPID-12 after administration of lidocaine alone, heparin alone, and placebo as determined by using the 11-point NRS for bladder pain. The IDMC will establish the exact primary endpoint based on the data recorded during the run-in phase of the study. The SPID score that is not determined by the IDMC as the primary endpoint will be considered the first secondary endpoint.

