On the day of study drug administration (V1a), subjects will be randomized (2:1:2:1); URG101:placebo:lidocaine:heparin) and will receive a single administration of one of four intravesical treatments in a blinded fashion, based on random assignment:

1. Combination product, URG101 (buffered heparin-lidocaine)
2. Placebo: [REDACTED]
3. Lidocaine: [REDACTED]
4. Heparin: [REDACTED]

Subjects will be monitored for 2 hours in the clinic after study drug administration.

CLINICAL PROTOCOL SYNOPSIS (continued)

	
Subjects will maintain a urination log and symptom diary after discharge and will return to the clinic the following day to complete the in-clinic study procedures and collection of the study diary.
 
The following will be completed according to the schedule of assessments over a 24-hour period after study drug administration: the 11-point NRS for bladder pain and urgency; the PORIS questionnaire; vital signs assessments; blood samples for safety laboratory assessments, i.e. blood coagulation (prothrombin time [INR] and activated partial thromboplastin time [aPTT]), and plasma lidocaine concentrations; adverse events; and concomitant medication assessments.
 
Subjects will be contacted within 48 to 72 hours after the last study treatment to follow-up on any ongoing adverse events after the last clinic visit.
 
The clinical study will plan to randomize 180 subjects. After 90 (50%) subjects have been enrolled and treated, the IDMC will examine the conditional power and determine if a modification to the sample size is required to yield an overall power of 90%. An adjustment to the type 1 error rate will not be necessary if the conditional power is >39% at the interim assessment.
 
The IDMC will consist of 3 members: 1 physician expert in IC/BPS, 1 expert in clinical development, and a biostatistician. None of the IDMC members will be associated with study personnel; all communication between the IDMC and study personnel will be pre-defined and governed by the IDMC charter. The IDMC will have access to unblinded pain scores to perform their ranking of the pain endpoints and for assessment of conditional power.

Estimated Number of Subjects:	A target of 180 subjects subject to adjustment by the IDMC. A maximum of 300 subjects will be enrolled in Study URG101-105.
Number of Study Sites:	Up to 30 sites in the United States and Canada

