9.1.6 Interim Study Analysis

After recruitment and treatment of the first ~90 (50%) of the planned 180 subjects, the IDMC will examine the conditional power and determine if a modification to the sample size up to 300 subjects is required to yield an overall power of 90%. An adjustment to the type 1 error rate will not be necessary if the conditional power is >39% at the interim assessment.

The IDMC will consist of 3 members: 1 physician expert in IC/BPS, 1 expert in clinical development, and a biostatistician. None of the IDMC members will be associated with study personnel; all communication between the IDMC and study personnel will be pre-defined and governed by the IDMC charter. The IDMC will have access to unblinded pain scores to perform their assessment of conditional power.

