9.7.1.1 Primary Endpoint

The primary endpoint for the investigative phase of the study is the sum of bladder pain intensity differences from baseline to 12 hours (SPID-12) after administration of URG101 compared with the SPID-12 after administration of lidocaine alone, heparin alone, and placebo as determined by using the 11-point NRS for bladder pain.

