9.7.1.2 Secondary Endpoints

The secondary endpoints of the study are:

1. The sum of bladder pain intensity differences from baseline to 24 hours (SPID-24) after administration of URG101 compared with lidocaine alone, heparin alone, and placebo as determined by using the 11-point bladder pain NRS
2. The sum of urgency intensity differences from baseline to 12 and 24 hours (SUID-12 and SUID-24) after administration of URG101 compared with lidocaine alone, heparin alone, and placebo using the 11-point urgency NRS
3. Absolute and percentage change in bladder pain from baseline to 1, 12, and 24 hours after administration of URG101 compared with lidocaine alone, heparin alone, and placebo as determined by using the 11-point NRS for bladder pain
4. Absolute and percentage change in urgency intensity from baseline to 1, 12, and 24 hours after administration of URG101 compared with lidocaine alone, heparin alone, and placebo using the 11-point urgency NRS
5. Patient Global Assessment: Comparison of the percentage of subjects achieving $\geq 50\%$ improvement in the PORIS questionnaire, Question 3, from baseline to 1 hour, 12 hours and 24 hours after administration of URG101, lidocaine alone, heparin alone, and placebo
6. Time to first administration of rescue medication for pain after treatment with URG101 compared to alkalinized Lidocaine Hydrochloride Injection (20 mg/mL) alone, alkalinized Heparin Sodium Injection (5,000 USPU/mL) alone, and placebo [REDACTED])
7. To evaluate the safety and tolerability of intravesical administration of URG101

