9.7.3 Determination of Sample Size

Sample size estimates were based on a pilot trial of heparin-lidocaine versus lidocaine alone and a prior two-arm study of URG101 versus placebo. The primary efficacy endpoint is SPID-12. The sample size calculation is based on a one-way analysis of variance, comparing SPID-12 from four treatment groups. A target sample size of approximately 180 subjects allocated among the four treatment groups. This sample size will be sufficient to achieve 90% power to detect a difference between the URG101 and components groups assuming a treatment effect size of 0.60. Once 50% of the subjects (90) have been enrolled, an unblinded interim assessment will be performed. The number of subjects for the study may be increased, based on the recommendation of the IDMC. Overall, a maximum of 300 subjects will be enrolled in Study URG101-105.

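### Section 8.1 lets the IDMC set the primary endpoint from run-in data, while the synopsis and sections 9.7.1.1 and 9.7.3 fix SPID-12 and no visible text describes a run-in

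*Combined protocol and SAP*

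**What the plan says.** Section 8.1 (Primary Objective) begins with SPID-12 and continues: "The IDMC will establish the exact primary endpoint based on the data recorded during the run-in phase of the study". It then settles what happens to the other candidate: "The SPID score that is not determined by the IDMC as the primary endpoint will be considered the first secondary endpoint". Only two SPID scores are defined in the protocol, SPID-12 and SPID-24, so the choice is between those two.

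Elsewhere the primary endpoint is not open. The synopsis gives SPID-12 under objectives, under criteria for evaluation and under sample size. Section 9.7.1.1 says "The primary endpoint for the investigative phase of the study is the sum of bladder pain intensity differences" and specifies the 12-hour window. Section 9.7.3 says "The primary efficacy endpoint is SPID-12". Section 9.7.1.2 lists as its first secondary endpoint: "The sum of bladder pain intensity differences from baseline to 24 hours (SPID-24) after administration of URG101".

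The IDMC's task is worded in two ways. The synopsis (Study Design) says "The IDMC will have access to unblinded pain scores to perform their ranking of the pain endpoints and for assessment of conditional power". Section 9.1.6 has the matching sentence without the ranking: "The IDMC will have access to unblinded pain scores to perform their assessment of conditional power".

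A few other traces of two phases remain. The table of contents titles section 9.1.6 as a run-in analysis, although the heading in the body is Interim Study Analysis. The synopsis limits the ITT set to an *investigative phase* and refers to *both phases* in the safety set, and section 9.7.1.1 also uses *investigative phase*. The set definitions in section 9.7.1.5 mention no phases.

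**The concern.** A primary endpoint cannot be both fixed in the analysis section and still to be established by a committee in the primary objective. As it stands, section 8.1 also cannot be carried out: the visible text gives no run-in size, population, timing or selection rule.

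What is at stake is pre-specification of the endpoint on which the trial's claim rests. Read literally, section 8.1 allows the primary endpoint to be set after data have been seen, by a body with access to unblinded pain scores, and nothing visible controls the error of that choice. The analysis sets are touched too. If a run-in existed, the synopsis would leave its subjects out of the ITT set, while section 9.7.1.5 would include every randomized and dosed subject.

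**Working it through.** **1. The passages side by side.**

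| Place | Primary endpoint | Open to change? |
|---|---|---|
| Synopsis (objectives, criteria for evaluation, sample size) | SPID-12 | No |
| 8.1 | SPID-12, then the IDMC's choice from run-in data | Yes |
| 9.7.1.1 | SPID-12 | No |
| 9.7.3 | SPID-12 | No |

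Sections 9.1 to 9.1.6 run from screening to randomization, dosing, home assessment, follow-up and one interim look at about 90 of 180 subjects. The visible recommendations in section 9.7.4 are to continue to target, to increase the sample size, or to stop for futility. None is a choice of endpoint. The limits on this check are that part of the synopsis design text and most of section 9.7.4 are blacked out, the body of Table 4 is not shown, and the IDMC charter is not among the documents.

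**2. The plan's own figure.** The synopsis states 90% power with allocation 60/30/60/30 at two-sided 0.05. (Section 9.7.3 words the effect sizes differently, which is a separate matter.) The noncentrality is d / √(1/n₁ + 1/n₂).

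- URG101 v lidocaine, 60 v 60, d = 0.60: 0.60 / 0.1826 = 3.29, power 90.3% (two-sample t).
- URG101 v placebo or heparin, 60 v 30, d = 0.75: 0.75 / 0.2236 = 3.35, power 91.3%.

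The stated 90% is reproduced. The sizing is stated for SPID-12, so removing the section 8.1 sentences leaves N = 180 unchanged.

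**3. What a literal reading could do to the error rate.** None of the following inputs except the 90-of-180 look, the alpha level, the assessment times and the baseline covariate is in the documents.

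Assume that the endpoint with the larger interim z at information fraction t = 90/180 = 0.5 becomes primary, that those subjects stay in the final test, and that one comparison is null for both endpoints. A two-sided 0.05 test that must favour URG101 has a nominal one-sided error of 2.5%. Let r be the correlation between SPID-12 and SPID-24, Z the final statistic of one endpoint, and D its standardized interim lead over the other. Then

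corr(Z, D) = √(t(1 − r)/2), and error = 2 × P(Z > 1.96, D > 0).

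For r, take trapezoid sums over the protocol's assessment times (0.5, 1, 2, 4, 6, 8, 10, 12 and 24 h), with baseline subtracted. Assume that the pain scores have either an equal correlation of 0.3-0.8 or a correlation decaying with a half-life of 4-24 h. Conditioning on baseline pain, because the model in section 9.7.1.14 has it as a covariate, gives r from 0.82 to 0.93.

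- r = 0.93: corr = √(0.5 × 0.07/2) = 0.132, error 3.1%.
- r = 0.82: corr = √(0.5 × 0.18/2) = 0.212, error 3.5%.

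Without the baseline adjustment the same model gives r of about 0.89-0.94 and an error of about 3.1-3.2%.

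**4. When there is no inflation.** If the run-in subjects are kept out of the final test, or the choice depends on something unrelated to the treatment contrast (missing data or pooled variability, for example), D carries no information about Z and the error stays at 2.5%.

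**The case against.** The strongest reply is that SPID-12 is plainly the working endpoint. Every analysis and sizing passage works without the two sentences in section 8.1, and the IDMC's visible options do not include choosing an endpoint. On that view this is editorial debris in a Phase 2a protocol. The explanation is likely, though it is an inference. It is a reason to delete the text, because the sentences are current and stand in the primary objective itself.

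A second reply carries more weight. If a run-in did exist, the synopsis wording that confines the ITT set to the investigative phase would point to run-in subjects being left out of the efficacy test, which is the case without inflation. Section 9.7.1.5 does not repeat that limit, so this is not conclusive. It does mean that the 3.1-3.5% scenario is not the reading the synopsis favours. It also means that the phase wording should not be removed before the sponsor confirms that there is no run-in, because it may be the only visible text separating those subjects.

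Third, SPID-24 as first secondary in section 9.7.1.2 might be read as a further contradiction. It is not one by itself, since section 8.1 predicts exactly that if SPID-12 is chosen. The conflict is that section 8.1 leaves open the roles that section 9.7 settles.

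Finally, the redactions mean that a run-in could be described in hidden text. They do not remove the conflict, because both sides of it are visible.

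**Conclusion.** The contradiction is real, stands in current text, and must be fixed: section 8.1 makes the primary endpoint a later IDMC decision, while the synopsis and sections 9.7.1.1 and 9.7.3 fix it as SPID-12. Confidence in this is high and depends on no calculation.

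A reader might infer that the trial's type I error is inflated, or that the IDMC will switch endpoints at the interim look. The documents support neither. They state no selection rule, do not equate the run-in with the first 90 subjects, and do not say that run-in subjects stay in the final test. The synopsis mentions ranking the pain endpoints, not choosing or replacing one. The increase from 2.5% to about 3.1-3.5% holds only if the choice uses unblinded data, favours the larger contrast, and keeps the same subjects, and it rests on an assumed correlation of 0.93 to 0.82. It is a modest, conditional caveat.

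**What to change.** 1. Delete the last two sentences of section 8.1. State there that SPID-12 is the sole primary endpoint and will not be changed on the basis of unblinded data.
2. In the synopsis (Study Design), remove the endpoint-ranking role so that the sentence on the IDMC's access to pain scores matches section 9.1.6.
3. Have the sponsor confirm whether a run-in exists. If it does not, correct the contents title of section 9.1.6 and remove the *investigative phase* and *both phases* wording from the synopsis and section 9.7.1.1, so that the analysis sets match section 9.7.1.5.
4. If a run-in choice is really intended, keep the phase separation and carry it into section 9.7.1.5. State the run-in size and the selection rule, and either exclude its subjects from the efficacy test or adjust alpha.

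Steps 1 to 3 cost wording only, and N = 180 stands. Step 4 is not free. The protocol gives no run-in size. If an assumed 18 of the 180 were excluded and not replaced, leaving 54/27/54/27, power would fall from 90.3% to 87.1% against lidocaine (effect 0.60) and from 91.3% to 88.2% against placebo or heparin (effect 0.75).

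The synopsis calls the interim analysis blinded under sample size, while section 9.7.3 calls it unblinded. That is a separate consistency point and should be corrected on its own.
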